	Each participant will be asked to provide a finger-prick blood sample for hemoglobin measurement, a rapid diagnostic test (RDT) for Plasmodium spp. and where applicable a biplex RDT for lymphatic filariasis/onchocerciasis at baseline and 6 and 12 months after treatment. At the same time points anthropometric measurements (i.e. height, weight, mid-upper arm circumference (MUAC) and skinfold thickness) will be taken for all participants. In addition, a venous blood sample (~8 ml) will be taken from each participant to assess biochemical blood parameters as proxies for vital organ functioning (e.g. complete blood count, urea, creatinine, transaminases etc.) and nutritional indicators for micro- (i.e. (pro-) vitamins, inflammation markers, and iron/ferritin) and macronutrient (i.e. albumin) deficiencies at baseline, day 21, day 180 and day 360.				
	To all participating households, a questionnaire will be administered assessing information on socioeconomic characteristics and access to sanitation, water facilities, and hygiene behavior.				
	For the assessment of pharmacokinetic parameters within the DF study the participating school-aged children (6-12 years) will be sampled using finger pricking for microsampling at 0, 1, 2, 3, 4, 5, 6, 7, 9, 24, 48 hours post-dosing.				
Statistical Analyses	An available case analysis will be performed, including all subjects with primary end point data. Supplementary, a per-protocol analysis will be conducted. CRs will be calculated as the percentage of egg-positive subjects at baseline who become egg-negative after treatment. Differences among CRs (between treatment arms and between diagnostic approaches) will be analysed by using crude and adjusted logistic regression modeling (adjustment for age, sex and weight).				
	Geometric and arithmetic mean egg counts will be calculated for the different treatment arms before and after treatment to assess the corresponding ERRs. Bootstrap resampling method with 5,000 replicates will be used to calculate 95% confidence intervals (CIs) for differences in ERRs.				

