	All stool samples will be examined with duplicated Kato-Katz thick smears for T. trichiura , A. lumbricoides and hookworm. S. stercoralis infections will be identified using the Baermann technique. For subsequent PCR-analysis a portion of 1.5-2 g of stool from each specimen will be preserved in 70% ethanol and shipped to a reference laboratory. From a subsample of 10 children with heavy intensity infections in each study setting an additional portion of stool (1.5-2 g) will be preserved in 95% ethanol, shipped to a reference laboratory and subjected to whole genome sequencing for characterization of Trichuris strains. Fecal occult blood and calprotectin in stool as markers for gut morbidity and inflammation will be detected using a rapid diagnostic test and an immunoassay, respectively. Individuals found positive 6 months after baseline will receive a second round of treatment according to their group scheme.
	Each participant will be asked to provide a finger-prick blood sample for hemoglobin measurement and co-infection with Wuchereria bancrofti at baseline and 6 and 12 months after treatment. At the same time points anthropometric measurements (i.e. height, weight, mid-upper arm circumference (MUAC) and skinfold thickness) will be taken for all participants. To all participating households, a questionnaire will be administered assessing information on socioeconomic characteristics and access to sanitation, water facilities, and hygiene behavior.
Statistical Analyses	An available case analysis will be performed, including all subjects with primary end point data. Supplementary, a per-protocol analysis will be conducted. CRs will be calculated as the percentage of egg-positive subjects at baseline who become egg-negative after treatment. Differences among CRs (between treatment arms and between diagnostic approaches) will be analysed by using crude and adjusted logistic regression modelling (adjustment for age, sex, community, weight and height).

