	follow-up prevalence will be determined 14-21 days, 6 months and 12 months post-treatment by collecting another two stool samples. Subjective treatment satisfaction will be assessed 3 hours, 3 weeks and 6 months after treatment to investigate relationship with treatment compliance and observed efficacy in reducing egg output and morbidity.
	All stool samples will be examined with duplicated Kato-Katz thick smears for T. trichiura , A. lumbricoides and hookworm. S. stercoralis infections will be identified using the Baermann technique and recorded qualitatively as larvae-positive or negative. Complementary to stool-based diagnostics, a small portion of urine from each participant will be fixed, transferred to a laboratory at Khon Kaen University in Thailand and examined for antibodies of S. stercoralis using a newly developed ELISA-based assay. For subsequent PCR and microbiome analysis of the stool samples a portion of 1.5-2 g from each specimen will be frozen and preserved in 70% ethanol, respectively and shipped to a reference laboratory at Swiss TPH in Switzerland. At baseline and in the first follow-up (3 weeks post treatment) an additional portion of stool (1.5-2 g) from a subsample of 10 participants identified with heavy intensity infections in each case and study setting will be preserved in 95% ethanol, shipped to the same reference laboratory and subjected to deep sequencing for characterization of T. trichiura strains and investigation of potential resistance markers. Fecal occult blood and calprotectin in stool as markers for gut morbidity and inflammation will be detected using a rapid diagnostic test and an immunoassay, respectively. A subsample of 30 participants will be asked to provide a daily stool sample for a period of up to 4 weeks to monitor dynamics of T. trichiura egg output for subsequent determination of the optimal timing for drug efficacy assessment. Individuals found T. trichiura positive 6 months after baseline will receive a second round of treatment according to their group scheme.

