	Each participant will be asked to provide a finger-prick blood sample for hemoglobin measurement and a rapid diagnostic test (RDT) for Plasmodium spp. at baseline and 6 and 12 months after treatment. At the same time points anthropometric measurements (i.e. height, weight, mid-upper arm circumference (MUAC) and skinfold thickness) will be taken for all participants. In addition, a venous blood sample (~8 ml) will be taken from each participant to assess biochemical blood parameters as proxies for vital organ functioning (e.g. complete blood count, urea, creatinine, transaminases etc.) measured in Laos and nutritional indicators for micro- (i.e. (pro-) vitamins, inflammation markers, and iron/ferritin) and macronutrient (i.e. albumin) deficiencies (evaluated in Switzerland) at baseline, day 21, day 180 and day 360. To all participating households (to any adult household member, ideally the household head), a household questionnaire will be administered assessing information on socioeconomic characteristics and access to sanitation, water facilities, and hygiene behavior.
Statistical Analyses	An available case analysis will be performed, including all subjects with primary end point data. Supplementary, a per-protocol analysis will be conducted. CRs will be calculated as the percentage of egg-positive subjects at baseline who become egg-negative after treatment. Differences among CRs

	(between treatment arms and between diagnostic approaches) will be analysed by using crude and adjusted logistic regression modeling (adjustment for age, sex, and weight).					
	Geometric and arithmetic mean egg counts will be calculated for the different treatment arms before and after treatment to assess the corresponding ERRs. Bootstrap resampling method with 5,000 replicates will be used to calculate 95% confidence intervals (CIs) for differences in ERRs.					
	Further secondary outcomes – as nutritional and morbidity indicators - will be analysed using logistic and linear regression as appropriate. To compare individual's changes in nutrition/morbidity categories as an effect from treatment McNemar's test will be applied. The analysis after 6 and 12 month of follow-up will be complemented by generalized estimating equation (GEE) models with independent correlation structure and empirical estimators to account for missing data.					

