- e) To compare CRs based on infection status determined by novel polymerase chain reaction (PCR)-based and standard microscopic diagnosis
- f) To assess potential differences in susceptibility to the treatment regimen between the three hookworm species, *Necator americanus, Ancylostoma duodenale* and *A. ceylanicum*, as classified through the novel PCR-based diagnosis
- g) To characterize *T. trichiura* strains from different epidemiological settings and investigate potential resistance markers using a deep sequencing analysis
- h) To determine optimal timing for measuring anthelmintic efficacy in T. trichiura infection
- i) To evaluate potential benefits from deworming on morbidity (clinically evaluated and self-rated from questionnaire interviews) on microbiome and nutritional indicators

4. Methodology

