At baseline, all participants will be asked to provide two stool samples of at least 15 grams each (within a maximum of 5 days). From every stool specimen, duplicate Kato-Katz thick smears (41.7 mg each) [15] will be prepared and read under a microscope for eggs of T. trichiura, A. lumbricoides and hookworm by experienced technicians. A small amount of feces (~10 mg and $60\mu g$, respectively) will further be tested on fecal occult blood and calprotectin as proxies for gut morbidity and inflammation using a rapid diagnostic test and an immunoassay, respectively [16]. Additionally, a portion of 1.5-2 g of stool from each specimen will be frozen and preserved in 70% ethanol, respectively and shipped to a reference laboratory at the Swiss Tropical and Public Health Institute (Swiss TPH, Basel, Switzerland) for microbiome and PCR analysis [17]. While discrimination of hookworm species via morphological comparison during microscopy of Kato-Katz slides is not feasible [18], PCR will allow to accurately determining efficacy and for further classification of hookworm infection into the three species N. americanus, A. duodenale and A. ceylanicum. The remains of each stool sample (ideally 10 to 20 g) will be processed by the Baermann technique for identification of S. stercoralis infections and be recorded qualitatively as larvae-positive or negative. Urine samples from each participant will be collected together with the 2nd stool sample, fixed and transferred to a laboratory at Khon Kaen University in Thailand for subsequent detection of S. stercoralis antibodies using a novel ELISA-based assay. At baseline and in the first follow-up (3 weeks post treatment) an additional portion of the second stool sample (1.5-2 g) from a

Page 146 of 176

subsample of 10 participants identified with heavy intensity infections in each case (as assed on the first sample) will be preserved in 95% ethanol, shipped to the same reference laboratory at Swiss TPH in Switzerland and subjected to deep sequencing for characterization of *T. trichiura* strains and investigation of potential resistance markers [19]. A subsample of 30 participants in each treatment arm will be asked to provide a daily stool sample for a period of up to 4 weeks to monitor dynamics of *T. trichiura* egg output for subsequent determination of the optimal timing for drug efficacy assessment as has been done for other STH species earlier [20].

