7.2 Justification of number of trial subjects

Based on available summarized efficacy measures from a recent review [1] and the published literature, we assume that the CR of albendazole against *T. trichiura* is 30% compared to 50% in the albendazole-ivermectin treatment regimen. To detect a difference with 90% power at a two-sided 5% significance level, we require 121 participants per study arm and 143 to account for potential loss to follow-up of 15%. We further assume the same treatment efficacy in the mid-term treatment and a 6-months reinfection risk of 10%. Consequently we expect a proportion of negative patients after 12 months of 44% in the albendazole arm and of 65% in the albendazole-ivermectin arm resulting in a required sample size of 111 participants per arm. To account for a loss to follow-up of 30% after 6 months and 40% at final assessment (12 months) we aim to recruit 300 participants in each treatment group (600 in total) in each country.

Subgroup analysis will be conducted stratifying the study population by age category (school-aged and adults). For the subgroup analysis we will pool the data from all 3 countries to ensure sufficient statistical power.

Page 155 of 176

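### PCR and Kato-Katz cure rates come from the same stools, but the synopses analyse their difference like that between independent arms, with no clustering on participant

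*Combined protocol and SAP*

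**What the plan says.** The Laos protocol, section 3, lists as secondary objective (e): "To compare CRs based on infection status determined by novel polymerase chain reaction (PCR)-based and standard microscopic diagnosis". The other country protocols have the same objective, with slightly different wording in Pemba.

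Both results come from one set of stools. Laos section 4.3.1 says of microscopy: "From every stool specimen, duplicate Kato-Katz thick smears (41.7 mg each". The Laos synopsis says of PCR: "For subsequent PCR and microbiome analysis of the stool samples a portion of 1.5-2 g from each specimen" is preserved and shipped. Section 4.3.1 repeats the same sampling and diagnosis at days 21, 180 and 360.

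The method is given only in the synopses, under Statistical Analyses. The Laos synopsis has, for differences in cure rates: "between treatment arms and between diagnostic approaches) will be analysed by using crude and adjusted logistic regression modeling". Pemba has: "Differences among CRs (between treatment arms and between diagnostic approaches) will be analysed by using crude and adjusted logistic regression modelling". The Swiss (EKNZ-approved) and Côte d'Ivoire protocols have the same sentence apart from spelling. The adjustment covariates are age, sex and weight, with community and height added in Pemba.

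The Laos synopsis defines the cure rate thus: "CRs will be calculated as the percentage of egg-positive subjects at baseline who become egg-negative after treatment".

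The SAP covers the data collected 3 weeks after treatment and keeps PCR infection status as a secondary endpoint. Its secondary objectives do not include the PCR/Kato-Katz comparison, and its efficacy table has no PCR row.

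**The concern.** Each participant contributes two correlated outcomes, cured by Kato-Katz and cured by PCR. The synopses give their difference the same model as the randomised arms, where each participant contributes one outcome. An analyst following the text would stack the two results per person and fit a logistic model that treats them as coming from different people. The crude cure rates would be right and their error bars wrong.

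The two tests look for the same infection in the same stool, so the correlation should be positive. The standard error of the difference is then too large, the interval too wide and the test conservative. What is at stake is the precision of a method comparison that the protocols list as an objective.

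**Working it through.** **1. Is there a paired method elsewhere?** Section 7.3 in the Swiss, Côte d'Ivoire and Laos protocols uses McNemar's test for nutrition and morbidity categories and ties GEE to the 6- and 12-month analyses. Pemba section 7.3 uses paired t-tests and GEE for morbidity indicators and McNemar's test for malnutrition categories. None covers the diagnostic comparison. The SAP's cure-rate methods are a two-group melded binomial test (unadjusted) and standard logistic regression (adjusted), with no statement on PCR against Kato-Katz.

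**2. Inputs.** The documents give no sample size, PCR cure rate or within-person correlation for this comparison, so there is no stated figure to reproduce. As a check on the inputs that are borrowed, section 7.2 assumes that the albendazole cure rate "is 30% compared to 50% in the albendazole-ivermectin treatment regimen", with 90% power at two-sided 5%:

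- n = (1.960 + 1.282)² × (0.3×0.7 + 0.5×0.5) / 0.2² = 120.8, so 121 per arm, as stated.
- 121 / 0.85 = 142.4, so 143, as stated.
- Recruitment is 300 per arm per country. Less 15%, this leaves 255.

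Assumed here: PCR cure rates below the Kato-Katz rates, within-person correlation phi of 0.3 to 0.7, and everyone in both denominators.

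**3. Standard error, one arm, n = 255, 50% against 40% cured.**

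- Treated as independent: √[(p₁q₁ + p₂q₂)/n] = √[(0.25 + 0.24)/255] = 4.38 points.
- Paired: √[(p₁q₁ + p₂q₂ − 2·phi·√(p₁q₁p₂q₂))/n], with √(0.25×0.24) = 0.245.

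| phi | Paired SE (points) | Independent SE / paired SE |
|---|---|---|
| 0.3 | 3.67 | 1.20 |
| 0.5 | 3.10 | 1.41 |
| 0.7 | 2.40 | 1.83 |

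The largest attainable phi for these two rates is √[(0.4×0.5)/(0.6×0.5)] = 0.816. A value of 0.8 would give a ratio of 2.24, but it sits almost at that limit, so the range stops at 0.7.

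**4. Type I error.** With equal true rates, the independent-sample z statistic has variance 1 − phi instead of 1. The actual level of a nominal 5% test is 2[1 − Φ(1.96/√(1 − phi))]: 1.9% at phi 0.3, 0.6% at 0.5 and 0.03% at 0.7. Simulating a logistic model on method and arm (2,000 datasets, 255 per arm) gave 1.8% and 0.55% at phi 0.3 and 0.5. With clustering on participant it gave 5.8% and 5.4%.

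**5. Power for a small difference.** Same model, 255 per arm, PCR 5 points lower in each arm (30% to 25%, 50% to 45%):

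| phi | Log-odds SE, ordinary | Log-odds SE, clustered | Power, ordinary | Power, clustered |
|---|---|---|---|---|
| 0.3 | 0.133 | 0.111 | 38% | 52% |
| 0.5 | 0.133 | 0.094 | 35% | 65% |

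A normal approximation agrees. The log-odds fall by about 0.251 in one arm and 0.201 in the other, averaging 0.226. Clustered power is Φ(0.226/0.111 − 1.96) = 53% and Φ(0.226/0.094 − 1.96) = 67%. Ordinary power is Φ[(0.226 − 1.96×0.133)/0.111] = 38% and, with 0.094 in the denominator, 36%.

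**6. Where it stops mattering.** For a 10-point difference (30% to 20%, 50% to 40%) at 255 per arm, simulated power is at least 97% by either analysis. For the 5-point difference pooled over three countries (3 × 255 = 765 per arm), it is 88% to 99% ordinary against 94% to 100% clustered, for phi from 0.3 to 0.8.

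**The case against.** The strongest reply is that a GEE or cluster-robust logistic model is still logistic regression, and that the authors handle repeated measurements correctly elsewhere, so the synopses may be under-specified and not wrong. This does not carry. Where the plan intends GEE with empirical variance estimators it says so, and the synopses cover both comparisons with one sentence that does not distinguish them.

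A reader might infer that the SAP applies a two-sample test to paired data. The documents do not support that. The SAP's melded binomial test and standard logistic regression belong to the between-arm analysis, and would be correct for PCR status compared by arm. On the diagnostic comparison the SAP has an omission, not a wrong method.

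A reader might also infer that objective (e) is badly underpowered. That is not established. The large losses need a small assumed difference, full pairing and analysis within one country. The documents do not say whether this comparison is by country or pooled, and pooling closes most of the gap. Nor does anything in the plan commit the authors to reading a non-significant difference as agreement between the tests.

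The point about full pairing stands as a limit on the figures. Enrolment requires Kato-Katz positivity, and the cure rate is defined for people who were egg-positive at baseline. If the PCR rate instead uses those PCR-positive at baseline, the two sets can differ and the data are only partly paired. The ratios above would then not apply exactly.

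**Conclusion.** The point holds, within limits. For objective (e) the synopses prescribe a method that ignores pairing, and nothing in section 7.3 or the SAP corrects it. The standard error is overstated by about 1.2 to 1.8 times for 50% against 40% cured, and the test is conservative. These sizes rest on assumed PCR cure rates, an assumed correlation of 0.3 to 0.7 and a common denominator. The direction rests only on the correlation being positive.

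The crude cure rates are unaffected, and so is the primary comparison of the arms. A reader might suspect spurious findings of a PCR/Kato-Katz difference, but the error runs the other way. The change should be made because it is specific and free, not because the trial's main conclusion depends on it.

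**What to change.** For objective (e), specify a logistic GEE or a logistic model with cluster-robust variance, with diagnostic method as a within-participant factor and clustering on participant. Fit it crude and then adjusted for the covariates already listed. This also copes with partly paired data.

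State which baseline-positive set is the denominator for the PCR cure rate.

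Add the comparison to the SAP with its method. The cost is analysis wording only; no new data or samples are needed.

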4.1 Primary and secondary endpoint

T. trichiura infection status assessed by Kato-Katz 14-21 days after treatment will be the primary endpoint and the main outcome for efficacy be expressed as CR (*i.e.* conversion from being egg positive pre-treatment to egg negative post-treatment) and ERR (secondary end point). Secondary endpoints include further infection status with *A. lumbricoides*, hookworm and *S. stercoralis* and related efficacy measures, adverse events and infection status assessed by PCR. In addition, optimal timing for drug efficacy assessment in *T. trichiura* infection will be determined, *T. trichiura* strains and the microbiome will be described and potential resistance markers evaluated using deep sequencing and potential benefits on nutritional and morbidity indicators from treatment assessed (exploratory end points).

4.2 Type of trial

Double blind randomized controlled trial.

4.3 Trial design

4.3.1 Baseline survey and screening

A randomized-controlled trial will be conducted with two treatment arms to be followed-up over a 12 months period with an intermediate re-treatment of participants found re-infected after 6 months (Figure). This parallel group trial will be conducted as a multi-country study; thus, in each setting a separate trial according to the design described below will be set up, to provide a better basis for the subsequent generalization of its findings. This arises from the possibility of recruiting the subjects from a wider population and of administering the medication in a broader range of clinical settings, thus presenting an experimental situation that is more typical of future use. The study includes one baseline and three follow-up assessments at 3 weeks (day 21), 6 months (day 180), and 12 months (day 360).
Page 145 of 176

Figure 2. Design and timeline of the randomized-controlled trial to be implemented in each of three settings.

The study is designed as a two-armed trial including one arm with a single drug administration (arm A; albendazole) and one arm with combined treatment through co-administration of separate tablets (arm B; albendazole and ivermectin).

The trial will be conducted as a multi-country study with two settings in Africa and one in Asia, namely Côte d'Ivoire, Pemba (Zanzibar, Tanzania) and Lao PDR.

At baseline, all participants will be asked to provide two stool samples of at least 15 grams each (within a maximum of 5 days). From every stool specimen, duplicate Kato-Katz thick smears (41.7 mg each) [15] will be prepared and read under a microscope for eggs of T. trichiura, A. lumbricoides and hookworm by experienced technicians. A small amount of feces (~10 mg and $60\mu g$, respectively) will further be tested on fecal occult blood and calprotectin as proxies for gut morbidity and inflammation using a rapid diagnostic test and an immunoassay, respectively [16]. Additionally, a portion of 1.5-2 g of stool from each specimen will be frozen and preserved in 70% ethanol, respectively and shipped to a reference laboratory at the Swiss Tropical and Public Health Institute (Swiss TPH, Basel, Switzerland) for microbiome and PCR analysis [17]. While discrimination of hookworm species via morphological comparison during microscopy of Kato-Katz slides is not feasible [18], PCR will allow to accurately determining efficacy and for further classification of hookworm infection into the three species N. americanus, A. duodenale and A. ceylanicum. The remains of each stool sample (ideally 10 to 20 g) will be processed by the Baermann technique for identification of S. stercoralis infections and be recorded qualitatively as larvae-positive or negative. Urine samples from each participant will be collected together with the 2nd stool sample, fixed and transferred to a laboratory at Khon Kaen University in Thailand for subsequent detection of S. stercoralis antibodies using a novel ELISA-based assay. At baseline and in the first follow-up (3 weeks post treatment) an additional portion of the second stool sample (1.5-2 g) from a

Page 146 of 176

subsample of 10 participants identified with heavy intensity infections in each case (as assed on the first sample) will be preserved in 95% ethanol, shipped to the same reference laboratory at Swiss TPH in Switzerland and subjected to deep sequencing for characterization of *T. trichiura* strains and investigation of potential resistance markers [19]. A subsample of 30 participants in each treatment arm will be asked to provide a daily stool sample for a period of up to 4 weeks to monitor dynamics of *T. trichiura* egg output for subsequent determination of the optimal timing for drug efficacy assessment as has been done for other STH species earlier [20].

A subsequent independent quality control of sample results (approximately 10%) will be conducted. Results are considered correct if the following tolerance margin is not exceeded: (i) No difference in presence/absence of hookworm, *A. lumbricoides* and *T. trichiura*, (ii) egg counts are +/-10 eggs for counts \leq 100 eggs or +/-20% for counts >100 eggs (for each species separately) [21]. In case discrepancies above the tolerance margin are noted in one or more slides, all slides are re-read by the local technicians. The new results are discussed, so that in case of discordant results, slides can be re-evaluated to reach consensus. Infection intensity expressed as the arithmetic and geometric mean egg count per gram of stool (EPG) will be calculated for each treatment arm. All microscopically analyzed quadruplicate Kato-Katz thick smears will be destroyed within one day (after passing the quality control). The same sampling procedure and diagnostic approach will be applied at days 21, 180 and 360 post-treatment.

In the Asian setting potential complications through albendazole treatment in patients affected by (neuro-) cysticercosis due to infection with *Taenia solium* have to be considered and communities without pig-farming activities should be prioritized for study location selection [22].

